
1.3.3.2. Triple-Negative Breast Cancer (TNBC)

The most common systemic therapies for the treatment of advanced/metastatic TNBC are platinum- and taxane-containing chemotherapy regimens. However, disease progression and/or recurrences develop quickly in vast majority of subjects with TNBC. Treatment with single agent pembrolizumab has demonstrated low to modest activity in subjects with TNBC positive for programmed cell death ligand 1 (PD-L1) who were previously treated (ORR 5.7%, disease control rate 9.5%) and previously untreated (ORR 21.4%) ([Adams, 2019a](#))([Adams, 2019b](#)).

In addition, atezolizumab had previously received accelerated FDA approval for treatment of subjects with unresectable locally advanced or metastatic TNBC with positive PD-L1 expression based on improved PFS with atezolizumab in combination with nab-paclitaxel compared with placebo plus nab-paclitaxel ([Schmid, 2018](#)). However, a confirmatory study (Impassion131) evaluating atezolizumab in combination with paclitaxel (i.e., non-protein bound) was negative ([Miles, 2020](#)).

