Similar progress was made in the treatment of metastatic MCC, where PD-1/PD-L1-blocking antibodies have demonstrated objective response rates 39-56% in treatment-naïve subjects ([Nghiem, 2016](#))([Nghiem, 2018](#))([D'Angelo, 2018](#)). For recurrent MCC, a case report describes a partial response to recombinant interferon- α 2a + topical imiquimod cream ([Wahl, 2016](#)). In the dose escalation portion of the phase 1 study of TLR9 agonist cavrotolimod in combination with pembrolizumab, 2 objective responses were observed in advanced MCC subjects with prior disease progression during or after prior anti-PD-1 therapy. Therefore, the combination of cemiplimab + vidutolimod is an appropriate study option for MCC subjects in both the PD-1 naïve and PD-1 resistant settings.

Basal Cell Carcinoma (BCC)

For subjects with locally advanced BCC, orally administered hedgehog pathway inhibitors (HHIs) such as vismodegib and sonidegib produce objective response rates of 48-56% in pivotal studies ([Sekulic, 2015](#))([Dummer, 2016](#)), and the reported response rate for vismodegib in the real-world setting is 68% ([Basset-Seguin, 2017](#)). However, these treatments are associated with adverse events such as muscle spasms, dysgeusia, alopecia, and weight decrease. Because approximately half of advanced BCC subjects do not respond to HHIs, and because the safety profile of these agents can be difficult for some subjects, new treatment options are needed.

BCC has similar clinical risk factors as CSCC and is also a hypermutated tumor ([Chalmers, 2017](#))([Yarchoan, 2017](#))([Nehal, 2018](#)). Cemiplimab produces an ORR of 31% in locally advanced BCC subjects in the second line after HHI inhibitors and is approved therapy in this setting ([Stratigos, 2021](#)).

Vidutolimod merits study in BCC for several reasons. As with CSCC, it is a tumor type that is responsive to interferon- α ([Chimenti, 1995](#)). In a pilot study of the TLR9 agonist PF-3512676, local regressions were observed in all 5 BCC subjects, including four partial regressions and one complete regression ([Hofmann, 2008](#)). The topical TLR7 agonist imiquimod, which also induces production of Type 1 interferons, is approved therapy for superficial BCC but not for advanced BCC ([Geisse, 2002](#)). Therefore, the combination of vidutolimod + cemiplimab could enhance the activity of single agent cemiplimab in the first line setting and is of interest as an investigational option for advanced BCC subjects.

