1.3.3.3. Non-Small Cell Lung Cancer (NSCLC)

Immune checkpoint inhibitors have revolutionized the treatment of NSCLC. PD-L1 is an important biomarker for selection of subjects more likely to respond to immunotherapy. Among subjects with newly diagnosed advanced NSCLC with PD-L1 CPS of at least 50% and without EGFR, ALK, or ROS1 genomic alterations, cemiplimab has demonstrated durable objective response rate (ORRs) of approximately 40% and superiority over chemotherapy in improving progression-free survival and overall survival ([Sezer, 2021](#)). Other checkpoint inhibitors (pembrolizumab, atezolizumab) have also demonstrated improved efficacy compared to platinum-based chemotherapy, as first line monotherapy in advanced NSCLC patients with high PD-L1 expression (CPS $\geq 50\%$) ([Reck, 2016](#))([Herbst, 2020](#)). In terms of OS, Cemiplimab ranked highest compared to atezolizumab and pembrolizumab ([Majem, 2021](#)). However, there are limited non-chemotherapy treatment options for subjects PD-L1 high NSCLC subjects who do not respond or progress after the initial response to anti-PD-1 therapy.

A clinical trial (CMP-001-003) has evaluated vidutolimod in combination with atezolizumab with and without radiation therapy in subjects with PD-1/PD-L1 blockade-resistant NSCLC ([Negrao, 2022](#)). On this study, intratumoral injections of vidutolimod were administered safely and successfully, including injection of visceral lesions.

No objective responses were observed in this heavily pretreated NSCLC patient population, but two subjects had tumor shrinkage (<30% decrease in tumor size, nonirradiated) and this correlated with strong induction of CXCL10. Study CMP-001-003 demonstrated the feasibility of IT therapy in NSCLC, and the lack of efficacy in the PD-1 refractory setting does not preclude possible meaningful antitumor activity in immunotherapy naïve patients. Vidutolimod in combination with standard cemiplimab warrants further development and evaluation in NSCLC in the favorable population of newly diagnosed advanced NSCLC patients with high PD-L1 expression ($\geq 50\%$), with disease that is amenable to IT injections.

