3.5. Subject Inclusion Criteria

Subjects enrolled into this study must meet the following inclusion criteria to be eligible.

1. Histopathologically-confirmed diagnosis of cancer that is metastatic or unresectable at Screening.
 - Subjects with metastatic or locally and/or regionally advanced unresectable CSCC.
Note 1: CSCC subjects without radiographically measurable disease are not excluded if there is at least 1 lesion ≥ 10 mm in at least 1 dimension documented by color photography.
Note 2: Subjects with tumors that arise in the setting of chronic inflammation (Marjolin's ulcer) such as chronic wounds and/or scars are excluded.
 - **Cohort A1:** Subjects who have not received prior systemic therapy for CSCC and who are not eligible for curative radiation.
 - **Cohort A2:** Subjects who have progressed while receiving a PD-1-blocking antibody or within 12 weeks of discontinuation. PD-1-blocking antibody treatment may have been administered in the adjuvant and/or neoadjuvant and/or locally advanced or metastatic setting.
 - Subjects with metastatic or locally and/or regionally advanced unresectable MCC.
Note: MCC subjects without radiographically measurable disease are not excluded if there is at least 1 lesion ≥ 10 mm in at least 1 dimension documented by color photography./

- **Cohort B1:** Subjects who have not received prior systemic therapy for MCC.
- **Cohort B2:** Subjects who have progressed while receiving a PD-1-blocking antibody or within 12 weeks of discontinuation. PD-1-blocking antibody treatment may have been administered in the adjuvant and/or neoadjuvant and/or locally advanced or metastatic setting.
- **Cohorts C1 and C2:** Previously treated subjects with advanced or metastatic TNBC must have disease that is HER2-negative, estrogen and progesterone receptor-negative, or < 5% expression based on American Society of Clinical Oncology/College of American Pathologists guidelines ([Hammond, 2010a](#))[\(Hammond, 2010b\)](#)[\(Wolff, 2013\)](#). Subjects with disease recurrence or progression following neoadjuvant or adjuvant therapy are eligible. Subjects with advanced or metastatic disease may have up to 5 lines of systemic therapy. Patients must have previously received treatment with sacituzumab govitecan (all TNBC patients), with trastuzumab deruxtecan (HER2-low patients) and with PARP inhibitor (for BRCA) patients.
 - **Cohort C1:** Subjects who have not received prior therapy with iCPIs.

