8.1. Sample Size Justification

The study is conducted as an exploratory trial. Each cohort of A1, A2, B1, B2, C1, C2, D, E, and F, will enroll approximately 25 subjects. The total number of subjects to be enrolled into this study is approximately 225. Based on historical data, the ORR of available treatment for each disease in Cohort is listed in [Table 12](#). If the observed ORRs in these Cohorts A1, A2, B1, B2, C1, C2, D, E, and F are as listed in [Table 12](#), then the lower bound of 90% confidence interval of ORR is listed in the table below.

Table 12: ORR of Available Treatment by Cohort

Cohort	ORR of Available Treatment	Observed ORR ≥	Lower Bound of 90% Confidence Interval
A1	50%	72%	>50%
A2	<10%	24%	>10%
B1	50%	72%	>50%
B2	<10%	24%	>10%
C1	21%	40%	>21%
C2	<10%	24%	>10%
D	50%	72%	>50%
E	39%	60%	>39%
F	19%	40%	>21%

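### Should the 21% reference response rate for cohort C1 be replaced, given that it matches only the protocol's rate for previously untreated TNBC?

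*Protocol*

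**What the plan says.** Protocol 8.1 plans about 25 subjects per cohort and introduces Table 12 with the words "Based on historical data, the ORR of available treatment for each disease in Cohort is listed in" that table. SAP 2.2 and its Table 1 repeat the figures. Row C1 reads: available-treatment ORR 21%, observed ORR at least 40%, lower bound of the 90% confidence interval above 21%. No citation, treatment or population is attached to any row.

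The only TNBC response rates in either document are in Protocol 1.3.3.2. They are for single-agent pembrolizumab in PD-L1-positive subjects "who were previously treated (ORR 5.7%, disease control rate 9.5%) and previously untreated (ORR 21.4"%). The same section names chemotherapy as the usual treatment, "The most common systemic therapies for the treatment of advanced/metastatic TNBC are platinum- and taxane-containing chemotherapy regimens", but gives no response rate for it.

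Protocol 3.5 defines the population: "Previously treated subjects with advanced or metastatic TNBC must have disease that is HER2-negative", and "Patients must have previously received treatment with sacituzumab govitecan (all TNBC patients"). Up to five lines of systemic therapy are allowed in advanced disease. C1 is then the group "Subjects who have not received prior therapy with iCPIs". There is no PD-L1 requirement for C1.

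SAP 1.2 states that there is no formal hypothesis and that the analyses are descriptive and exploratory. The protocol synopsis mentions exact binomial testing of the ORR but gives no null value for it. Protocol 8.6.1 and SAP 7.2.1 report the ORR with a 95% Clopper-Pearson interval.

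**The concern.** The 21% looks as if it was taken from the wrong line of therapy. Only 21.4% rounds to it, and that rate belongs to previously untreated subjects, whom C1 excludes. The rate quoted for previously treated subjects is 5.7%, so the listed reference is about 3.7 times as high (21 / 5.7). Some other rows do fit their own line of therapy. B1's 50% lies within the range for treatment-naive MCC, where PD-1/PD-L1 antibodies "have demonstrated objective response rates 39-56% in" such subjects. E's 39% is close to the figure for newly diagnosed NSCLC, where "cemiplimab has demonstrated durable objective response rate (ORRs) of approximately 40"%.

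C1 has no control arm, so this row is its only stated yardstick. If the proper reference were well below 21%, a reader who treats 40% as a pass mark could dismiss a result of, say, 7 or 8 responders out of 25 as no better than available treatment when it is better. The error would run toward missing activity, not toward overstating it.

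**Working it through.** **Inputs.** n = 25 per cohort (Protocol 8.1). Reference 21%, observed ORR 40%, 90% interval (Table 12, row C1). Planned reporting interval 95% Clopper-Pearson (Protocol 8.6.1, SAP 7.2.1). The table does not name its interval method; two-sided Clopper-Pearson is assumed here.

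**Formula.** The lower bound for x responders out of n is the α/2 quantile of a Beta(x, n − x + 1) distribution, with α = 0.10 for the table and α = 0.05 for the planned report.

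**The plan's own row.** 40% of 25 is 10 responders. The 90% lower bound for 10/25 is 23.6%, above 21%. For 9/25 it is 20.2%, below 21%. Row C1 is therefore correct, and 10 is the smallest count that clears 21%.

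**The other rows.** 18/25 (72%) gives 53.8%, above 50%. 6/25 (24%) gives 11.0%, above 10%. 15/25 (60%) gives 41.7%, above 39%. Row F lists 40% against a reference of 19%, but 9/25 (36%, bound 20.2%) would already clear 19%. The listed observed ORR is thus the smallest clearing count in eight of nine rows, and the table nowhere says that it has to be.

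**How the count moves with the reference.**

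| Responders of 25 | ORR | 90% lower bound | 95% lower bound |
|---|---|---|---|
| 4 | 16% | 5.66% | 4.5% |
| 5 | 20% | 8.2% | 6.8% |
| 6 | 24% | 11.0% | 9.4% |
| 7 | 28% | 13.9% | 12.1% |
| 8 | 32% | 17.0% | 14.95% |
| 9 | 36% | 20.2% | 18.0% |
| 10 | 40% | 23.6% | 21.1% |

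On the 90% reading, a reference of 20% needs 9, 15% needs 8, 10% needs 6 and 5.7% needs 5 (the bound for 4/25, 5.66%, falls just short). On the planned 95% interval, 20% needs 10, 15% needs 9 and 10% needs 7. At a 20% reference the listed 40% therefore stands unchanged under the interval that will be reported.

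**What a lower mark would do.** Binomial probability of reaching the count, for assumed true rates:

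| True ORR | at least 6 | at least 8 | at least 10 |
|---|---|---|---|
| 25% | 0.62 | 0.27 | 0.07 |
| 30% | 0.81 | 0.49 | 0.19 |
| 35% | 0.92 | 0.69 | 0.37 |

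These are chances of clearing a descriptive mark, not power. The price of the lowest mark is that 6 or more of 25 occurs with probability 0.03, 0.16 or 0.38 if the true rate is 10%, 15% or 20%.

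**Does the text show that 21% is the wrong number?** Row F's 19% is not among the rates in Protocol 1.3.3.4, so a table entry need not be quoted in the rationale. Row D's 50% fits the hedgehog-inhibitor rates in Protocol 1.3.3.1, yet D enrols subjects who decline or are not candidates for such a drug, so that row is a benchmark for the disease and not for a treatment its subjects would take. The column heading refers to available treatment, which for C1 could be chemotherapy, pembrolizumab or something else. The documents establish that 21% is unsourced. They do not establish that it is wrong.

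**The case for a change.** The strongest case for acting is that the repair is cheap and the gap is real. One row in each document would be annotated; if 21% has another source, the sponsor need only cite it; if it is meant as a cautious first-line benchmark, it can be labelled so. The listed value is also only 0.76 points above the 20.24% bound for 9/25, so a reference of 20% already moves the count by one. If the right figure is 10% or less, any result from 6 to 9 responders would have a 90% lower bound above it while falling short of the table's 40%.

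Most of this stands as a comment on documentation. It does not stand as a reason to change the plan. Putting in a different number needs a rate for previously treated, checkpoint-inhibitor-naive TNBC, and neither document has one. The 5.7% figure comes from PD-L1-positive subjects on one drug, whereas C1 is not PD-L1-selected. Entering it in the table's style (<10%, 24%, >10%) would make C1 identical to C2, although the table gives the PD-1-naive cohort the higher reference in all three pairs (A1/A2, B1/B2, C1/C2). The resulting mark of 6/25 would not clear 10% on the planned 95% interval (lower bound 9.4%). The misreading of 6 to 9 responders also requires someone to treat 40% as a pass mark, which the documents do not do.

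**Conclusion.** No change follows. Row C1 lacks a source, and the resemblance to the untreated rate is a fair reason to ask about it, but the row is arithmetically true and stays true for any lower reference: a 23.6% lower bound at 10/25 exceeds 20%, 15% or 10% as well as 21%. If the value is too high, the consequence is a descriptive mark one responder too strict at a 20% reference, two at 15% and four at 10%, on the 90% reading; on the 95% reading that will be reported it is zero, one and three. The error would be in the cautious direction.

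The sample size of 25 is common to all cohorts and does not come from this row. The reported ORR, its 95% interval and every secondary analysis are unaffected, and a reader can set that interval against whatever reference they consider right for C1. An analyst interpreting C1 would name the comparator when writing up, which fills the gap.

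This rests on three assumptions: the table uses two-sided Clopper-Pearson bounds, C1 reaches about 25 subjects, and the table stays descriptive as SAP 1.2 states. If a go/no-go rule were later tied to the 40% figure, the source of the 21% would need to be settled first.

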1.3.3.3. Non-Small Cell Lung Cancer (NSCLC)

Immune checkpoint inhibitors have revolutionized the treatment of NSCLC. PD-L1 is an important biomarker for selection of subjects more likely to respond to immunotherapy. Among subjects with newly diagnosed advanced NSCLC with PD-L1 CPS of at least 50% and without EGFR, ALK, or ROS1 genomic alterations, cemiplimab has demonstrated durable objective response rate (ORRs) of approximately 40% and superiority over chemotherapy in improving progression-free survival and overall survival ([Sezer, 2021](#)). Other checkpoint inhibitors (pembrolizumab, atezolizumab) have also demonstrated improved efficacy compared to platinum-based chemotherapy, as first line monotherapy in advanced NSCLC patients with high PD-L1 expression (CPS $\geq 50\%$) ([Reck, 2016](#))([Herbst, 2020](#)). In terms of OS, Cemiplimab ranked highest compared to atezolizumab and pembrolizumab ([Majem, 2021](#)). However, there are limited non-chemotherapy treatment options for subjects PD-L1 high NSCLC subjects who do not respond or progress after the initial response to anti-PD-1 therapy.

A clinical trial (CMP-001-003) has evaluated vidutolimod in combination with atezolizumab with and without radiation therapy in subjects with PD-1/PD-L1 blockade-resistant NSCLC ([Negrao, 2022](#)). On this study, intratumoral injections of vidutolimod were administered safely and successfully, including injection of visceral lesions.

No objective responses were observed in this heavily pretreated NSCLC patient population, but two subjects had tumor shrinkage (<30% decrease in tumor size, nonirradiated) and this correlated with strong induction of CXCL10. Study CMP-001-003 demonstrated the feasibility of IT therapy in NSCLC, and the lack of efficacy in the PD-1 refractory setting does not preclude possible meaningful antitumor activity in immunotherapy naïve patients. Vidutolimod in combination with standard cemiplimab warrants further development and evaluation in NSCLC in the favorable population of newly diagnosed advanced NSCLC patients with high PD-L1 expression ($\geq 50\%$), with disease that is amenable to IT injections.

1.3.3.4. Head and Neck (HPV-Positive)

HPV-positive OPSCC represents a distinct subset of HN cancer, at both the clinical and molecular levels ([Ferris, 2023](#)). In patients with oropharynx primary, HPV positivity can be established by a positive p16 immunohistochemistry (IHC) result. Alternatively, the presence of HPV E6/E7

mRNA transcripts in the tumor, as directly demonstrated by RNA ISH, can establish that an oropharynx SCC is HPV-positive ([Ferris, 2023](#)). A positive HPV DNA ISH result also establishes that an oropharynx primary tumor is HPV associated, although this test is less commonly used ([Gillison, 2016](#)). In HNSCC patients who present with cervical lymphadenopathy and occult primary, the diagnosis of HPV-associated disease with occult oropharynx primary is accepted when HPV positivity is documented by HPV RNA or DNA ISH ([NCCN, 2023](#)).

Patients with HPV-positive oropharynx squamous cell carcinoma (OPSCC) have lower risk of disease recurrence after curative intent therapy for locally advanced disease, compared to patients with HPV-negative oropharynx cancer ([Ang, 2010](#)). However, for patients who do experience recurrent or metastatic HPV-positive HNSCC and received pembrolizumab (either as monotherapy or in combination with chemotherapy), the median overall survival is less than 20 months ([Black, 2023](#)). Therefore, there is an urgent need for new treatment options for patients with R/M HPV-positive OPSCC.

In a phase 2 study, HNSCC patients received pembrolizumab + SD-101, a TLR9 agonist of CpG-C class, in the 1L R/M setting. Overall, the objective response rate (ORR) was 24% for all HNSCC patients. Among patients with HPV-positive disease, ORR was 44% (7/16). Among patients with HPV-negative disease, ORR was 12% (2/17) ([Cohen, 2022](#)). These findings are consistent with results in a phase 2 study of pembrolizumab + vidutolimod in 1L R/M HNSCC patients, which enrolled 6 patients with HPV-positive R/M OPSCC. Among these 6 patients, there was one durable partial response, and one near-partial response (-29% reduction in target lesions by RECIST) (NCT04633278; Regeneron data on file). In these two studies, there was no signal for enhanced efficacy with the addition of TLR9 agonist to pembrolizumab in HPV-negative patients, compared with historical experience with pembrolizumab monotherapy in 1L R/M HNCC ([Burtness, 2019](#)). The mechanistic basis of potential enhanced efficacy of TLR9 agonist in HPV-positive OPSCC has not been established, but plasmacytoid dendritic cells (pDCs) from HPV-positive OPSCC tumors may secrete immune-supportive cytokines such as IFNAlpha, whereas pDCs from HPV-negative tumors may secrete immune-suppressive cytokines such as IL-10 and TNFAlpha ([Koucký, 2021](#)).

The current study will evaluate cemiplimab + vidutolimod in R/M, PD-L1 CPS score ≥ 1 , HPV-positive OPSCC among patients who have not received prior systemic therapy for R/M disease.

1.3.4. Rationale for Doses and Schedules

1.3.4.1. Rationale for Vidutolimod Dose and Schedule

In the Phase 1b clinical study CMP-001-001, vidutolimod IT was evaluated at doses of 1 to 10 mg using 2 dosing schedules and with preparations containing 2 different concentrations of the excipient polysorbate 20 (0.01% and 0.00167%) in combination with pembrolizumab IV in subjects with PD-1 refractory melanoma. The safety profile was similar and manageable across the vidutolimod doses of 1 to 10 mg. Antitumor activity, as shown by durable CRs and PRs according to RECIST, was observed in 23% of subjects who initiated treatment with the proposed dose and schedule for this study: vidutolimod 10 mg (0.01% polysorbate 20) IT every week for 7 doses, followed by administration Q3W in combination with pembrolizumab 200 mg IV Q3W. This dose and schedule were selected for further development with PD-1-blocking antibodies. Further details can be found in vidutolimod IB.

1.3.4.2. Rationale for Cemiplimab Dose

Cemiplimab is currently approved as a monotherapy treatment at 350 mg IV Q3W for patients with metastatic or locally advanced CSCC who were not candidates for curative surgery or curative radiation, for the treatment of patients with metastatic BCC or locally advanced BCC who were previously treated with a HHI, and for the first-line treatment of patients with locally advanced or metastatic NSCLC whose tumors have high (tumor proportion score [TPS] $\geq 50\%$) PD-L1 expression. The approved dose will be utilized for this study.

1.4. Benefit-Risk

More detailed information about the known and expected benefits and risks, and reasonably expected adverse events may be found in the vidutolimod and cemiplimab IBs.

Included in this amendment are measures to account for the “Coronavirus Disease 2019” (COVID-19) pandemic and to minimize the risks to the patients in the study as well as healthcare providers by allowing flexibility in the visit schedule while social distancing suggestions are in place. Allowing for this flexibility does not increase the risk of participating in this study as there will be continued contact between the patients and study personnel despite postponement of in-person clinic visits.

The primary objective of this study is to evaluate the efficacy (ORR) of vidutolimod administered by IT injection in combination with cemiplimab IV in subjects with selected types of advanced or metastatic cancer.

A major mechanism of resistance to PD-1 blockade is the absence of activated effector T cells in the tumor. Therefore, activation of T cells by TLR9 agonism, and subsequent trafficking to tumor sites, has the potential to improve the response to PD-1 blockade, particularly in non-inflamed tumors. The efficacy of vidutolimod in combination with pembrolizumab has been demonstrated in patients with melanoma refractory to PD-1 blockade in the ongoing Study CMP-001-001. The objective response rate (ORR) was 27.6% (27/98; 95% CI 19.0%, 37.6%), including patients with responses after initial progressive disease (PD), and the best ORR by Response Evaluation Criteria in Solid Tumors Version 1.1 (RECIST v1.1) was 23.5% (23/98; 95% CI 15.5%, 33.1%), including 7 complete responses (CR) and 16 partial responses (PR). Additional details are provided in Section 1.3.1.3 and Section 5.4 of the vidutolimod IB. Rationale for combining vidutolimod with cemiplimab in various indications is described in Section 1.3.3.

Although vidutolimod has not been studied with cemiplimab except in this current study, the safety profile of vidutolimod in combination with other PD-1/PD-L1 agents is described below.

The analysis of available cumulative safety data from ongoing studies demonstrates a safety profile for vidutolimod in combination with pembrolizumab or nivolumab that predominantly consists of Grade 1 to Grade 2 AEs of flu-like symptoms (which can include, but may not be limited to, fever, nausea, vomiting, chills, and/or rigors; headache, tachycardia, rash, or hypoxia may also occur), cytokine release syndrome (CRS), hypotension, and injection site reactions. Treatment-related TEAEs involved events of chills, pyrexia, fatigue, nausea, vomiting, injection site pain, and headache. Commonly reported SAEs that have been observed across these clinical studies with vidutolimod were chills, pyrexia, fatigue, and hypotension.

The TEAEs of fever (pyrexia), chills, nausea, vomiting, diarrhea, headache, rash, and hypotension typically present after the second and subsequent vidutolimod doses and generally resolve within a few hours with supportive care. Stress dose corticosteroids may be required for hypotension unresponsive to IV fluids or in subjects that experience a prior Grade ≥ 3 vidutolimod-related event. Please refer to Vidutolimod IB Section 5.3 for a summary of all available cumulative safety data in the 6 studies.

In clinical studies, there is no evidence to suggest that vidutolimod in combination with a PD-1/PD-L1-blocking antibody or as monotherapy increases the frequency or severity of immune-related AEs.

No treatment-related Grade 5 TEAEs were reported across clinical studies.

Thus, taking into account the risk minimization measures outlined in this phase 2 protocol to minimize important risks to patients, the potential for therapeutic benefit and medical need for new combination therapy, the risk-benefit profile is anticipated to be positive for coadministration of vidutolimod, with cemiplimab, anti-PD-1, in the phase 2 study, in the population of subjects with selected types of advanced or metastatic cancer.

